6.7 Baseline Blood And Biomarker Specimen Collection

Please draw all normal blood tests as you would for your normal standard of care for the treatment of an aneurysmal subarachnoid hemorrhage. hsCRP and Anti-Xa levels will be drawn for all subjects after enrollment but prior to initiation of the study drug (for those subjects in the LDIVH treatment group).

Additional blood will be drawn and processed to plasma and stored for additional biomarker analysis. This may be performed up to 6 hours after initiation of study drug for the LDIVH arm (but preferably prior to study drug initiation). Please see the section below on the collection and processing of plasma biomarker specimens Section 6.11

If the subject already has an external ventricular drain or a lumbar drain placed, then removal of cerebrospinal fluid should be performed again with processing of the specimens for biomarker analysis. This may be performed up to 6 hours after initiation of study drug for LDIVH arm (but preferably prior to study drug initiation). Please see the section below on the collection and processing of CSF biomarker specimens Section 6.11.

6.8 Initiation Of Study Drug, Standard Dose Escalation, And Duration Of Infusion

Once the patient has been randomized, if the patient has been randomized to the LDIVH treatment arm then the study drug will be initiated 12 ± 4 hours following the completion of the aneurysm treatment procedure. The LDIVH infusion will initiate at 8 u/kg/hr. The date and time of study drug initiation will be recorded in the CRF. The control group will not receive any study infusions.

The LDIVH infusion (LDIVH group only) will be initiated at 8 u/kg/hr. This rate of heparin infusion should typically be escalated twice to reach the standard goal infusion rate of 12 u/kg/hr. There should be 12 hours between each dose adjustment. This escalation should result in an increase of the rate by 2u/kg/hr to a minimum target of 12u/kg/hr. A follow-up aPTT should be checked 6 hours after dose initiation and each dose adjustment. The goal rate for the LDIVH group should be **at least** 12 u/kg/hr, however if the aPTT is still below the lower limits of the acceptable range, then 12 hours after the last dose escalation, the rate can be again increased by 1u/kg/hr beyond the minimum of 12 u/kg/hr. (Max infusion rate of 1800 units/hr). Again, LDIVH target is at least 12 u/kg/hr while maintaining an aPTT value within the range that correlates with an Anti-Xa value of 0.1-0.3 u/ml.

Example: Site A initiates LDIVH on Patient X weighing 80kg. Target aPTT for Site A is 40-60 seconds.

LDIVH gtt is initiated at 8 u/kg/hr (640 u/hr) and an aPTT is obtained 6 hours later. aPTT result 6 hours later is 42 seconds. (Even though aPTT was 42, you will always try to get to a minimum of 12 u/kg/hr minimum as long as aPTT is not above the upper goal [60 in this example])

Dose escalation needed.

12 hours after LDIVH initiation, Patient X will have the LDIVH rate increased to 10u/kg/hr (800 u/hr).

aPTT result 6 hours later is 38 seconds

Dose escalation needed.

LDIVH gtt is escalated 12 hours after last dose adjustment (approximately 6 hours after most recent aPTT value) to 12 u/kg/hr (960 u/hr).

aPTT result 6 hours later is 39 seconds

Dose escalation needed.

LDIVH gtt is escalated 12 hours after last escalation (6 hours after aPTT value) to 13u/kg/hr (1040 units/hr)

aPTT result 6 hours later is 42 seconds

No further dose adjustments needed for this patient at this time.

Routine aPTT checked 24 hours later and result is now 36 seconds and Patient X remains at 13u/kg/hr

Dose escalation needed.

LDIVH gtt rate is escalated to 14 u/kg/hr (1200 units/hr)

aPTT 6 hours later is 45 seconds

No further dose adjustments needed for this patient at this time.

3-days have passed. The Routine aPTT checked every 24 hours is now 65 seconds and Patient X remains at 14 u/kg/hr.

Blood should be redrawn (paying close attention to technique) and a new aPTT should be obtained to confirm the aPTT is too high. If the aPTT recheck is again too high, the LDIVH dose rate must be decreased by 1-2 u/kg/hr depending on the aPTT value.
Dose decrease needed.

LDIVH gtt rate is decreased to 13 u/kg/hr (1040 units / hr)
aPTT 6 hours later is 58 seconds
No further dose adjustments needed for this patient at this time.

The duration of the LDIVH drug infusion will be 14 total days unless the patient is discharged from the acute care setting prior to the ability to complete the 14 days. It is not the intent of this protocol to extend the hospital stay in order to complete a full 14-day infusion. The LDIVH infusion can be given in the ICU setting or the non-ICU setting. The LDIVH infusion should not delay the transfer of the patient out of the ICU setting.

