STUDY DRUG NAME
AND FORMULATION**

Unfractionated Heparin (UFH) intravenous solution at a concentration of 100 units per ml (25,000 to 50,000 units of heparin in 250 to 500 ml of 0.9% or 0.45% NaCl solution)

INTENDED USE

A prophylactic infusion of LDIVH for up to 14 days with prescribed escalated dosing until the goal aPTT value is achieved. The LDIVH infusion is intended to prevent cognitive deficits in modified-Fisher grade 3 and 4 aneurysmal subarachnoid hemorrhage survivors following endovascular coil embolization of the ruptured cerebral aneurysm. The LDIVH infusion is to be initiated 12 ± 4 hours after coiling of the aneurysm. The infusion will be started at 8 units/kg/hr (0.08 cc/kg/hr) and increased by 2 units/kg/hr every 12 hours until the goal aPTT is reached (typically 12 u/kg/hr) *Note: The goal aPTT is an institution specific aPTT value that correlates with an anti-Xa assay value of 0.1 – 0.3 IU/ml of heparin.*

STUDY SUCCESS

For the purposes of this trial, study success is defined as demonstrating a statistically significant improvement in the mean MoCA score for the LDIVH arm compared to the control arm of the study at the 90-day follow-up visit or a significant reduction in inflammatory biomarker levels in the LDIVH arm compared to the control arm. In addition, there can be no significant differences between groups in the rate of Major Bleeding or Clinically Relevant Non-Major Bleeding attributable to the LDIVH treatment.

PATIENT COMPLETION

Patient completion in the study occurs when the patient has completed his/her 1-year follow-up

visit and all case report forms (CRFs) and Imaging required by the Study Protocol have been completed OR the patient has withdrawn from the study or has been determined to be “Lost to Follow-up” and all available CRFs and Imaging have been collected and submitted to the University of Louisville. The primary endpoint is the 90-day follow-up visit and therefore the primary data-analysis will occur after this date.

**PRIMARY PRINCIPAL
INVESTIGATOR (PPI) /
SPONSOR**

[name]
Associate Professor of Neurosurgery
Chief, Vascular Neurosurgery
University of Louisville School of Medicine
Louisville, KY
[contact];
[contact]

**CO-PRINCIPAL
INVESTIGATORS (Co-PI)**

J. [name], PhD
Professor of Neurosurgery, Pathology & Physiology
University of Maryland Medical Center
Baltimore, MD

[name]
Professor and Vice Chair for Education
Department of Neurosurgery
Director, Cerebrovascular Surgery Program

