5.2 Dose Selections And Treatment Duration

This study will plan to infuse the study drug UFH in an escalating fashion with a minimum target rate of 12 u/kg/hr and until a goal aPTT is achieved. The aPTT should be maintained at that level for up to 14 days of study drug infusion. The study drug infusion will begin 12 hours +/- 4 hours after the aneurysm treatment procedure is completed. **The initial infusion rate will be 8 units/kg/hr.** An aPTT will be checked 6 hours later and if a therapeutic level is not achieved the rate will be increased to 10 u/kg/hr 12 hours after study drug initiation. An aPTT level will again be checked 6 hours after the rate increase and the rate will be increased again by 2 u/kg/hr to 12 u/kg/hr, 12 hours after last adjustment until the aPTT goal is reached and then the study drug infusion will be maintained at that level with periodic aPTT levels being checked to confirm that the target aPTT is maintained. Additional upward dose rate adjustments after reaching 12 u/kg/hr (if needed) should be by 1u/kg/hr to avoid overshooting the aPTT goals which could increase the risk of hemorrhage. **The maximum hourly rate of the LDIVH infusion should be 1800 units / hour regardless of patient weight.**

The reason for the dose escalation is to mirror a previously reported protocol (Maryland LDIVH protocol) where LDIVH has been administered safely to over 100 aSAH patients treated with craniotomy and clipping without any hemorrhagic complications. The

divergence from that procedure (8 to 9 to 10 u/kg/hr) is to currently initiate the infusion at 8 units/kg/hr and then increase to 10 u/kg/hr and then again to 12 u/kg/hr. This modification was put into effect and is currently being used at the University of Maryland due to the recent (October 2009) reevaluation of UFH potency by the FDA and the United States Pharmacopeia (USP) that resulted in an approximate 10% reduction in heparin potency within the United States in October 2009 compared to previous years. [<http://www.fda.gov/Drugs/DrugSafety/PostmarketDrugSafetyInformationforPatientsandProviders/ucm184502.htm>]

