The other area of divergence is that the Maryland LDIVH protocol set a specific target infusion rate (10 or 12 units/kg/hr) regardless of the drug's effect on an individual patient. Variability in aPTT test values in these patients highlighted that the rate of metabolism of UFH varies among patients and therefore we expect the clinical effect to likewise vary among patients when a steady rate of infusion is maintained for all patients. **Our current protocol allows for adjustments of the rate of infusion up or down from 12 units/kg/hr to achieve a target aPTT for each patient that is institution specific and correlates with an anti-Xa heparin assay value of 0.1 – 0.3 IU/ml. The highest rate of heparin that consistently allows subjects at an institution to remain within the desired aPTT goal range is preferred such that the upper end of the target range is more desired over the lower end of the target range. Adjusting the rate by less than 1 unit/kg/hr is not allowed.** The anti-Xa values recommended for heparin anticoagulation therapy (for DVT or PE treatment therapy) are between 0.3 to 0.7 IU/ml. Therefore targeting aPTT values that correlate with 0.1 - 0.3 IU/ml anti-Xa values will provide a consistent, low-level, continuous systemic heparin effect while minimizing the risk of hemorrhagic complications. Routine adjusting of the LDIVH drip will be done with aPTT testing and not with Anti-Xa testing.

Maintaining the aPTT in the target range is important to avoid potential hemorrhagic complications while attempting to maximize the potentially beneficial anti-inflammatory effects of the study drug. Hemorrhagic complications could occur secondary to an anticoagulation effect in aSAH patients treated with coil embolization secondary to the femoral arteriotomy access site (i.e., risk of life threatening retroperitoneal hemorrhage) or inadequate embolization of the ruptured cerebral aneurysm, or secondary to ventriculostomy placement. The anticoagulation effect maintained below the anticoagulation therapeutic window should reduce the chance of a hemorrhagic complication in these subjects.

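### The worked dosing example in 6.8 prints 1200 units/hr where 14 u/kg/hr at 80 kg is 1120, and the synopsis and part of 5.2 stop escalation at the goal aPTT while 6.8 takes an in-range patient on to 12 u/kg/hr

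*Protocol*

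**What the plan says.** **The example.** Section 6.8 takes an 80 kg patient at a site whose aPTT target is 40 to 60 seconds. It prints 640, 800, 960 and 1040 units/hr for 8, 10, 12 and 13 u/kg/hr. The next step reads "LDIVH gtt rate is escalated to 14 u/kg/hr (1200 units/hr", and a later reduction returns the patient to 13 u/kg/hr, printed as 1040 units/hr. For increases above 12 u/kg/hr, section 5.2 says each one "should be by 1u/kg/hr to avoid overshooting the aPTT goals which could increase the risk of hemorrhage". Section 6.8 gives the same 1 u/kg/hr step.

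**The escalation rule.** It is stated in several places:

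- Section 1.1 (Intended Use): the rate is "increased by 2 units/kg/hr every 12 hours until the goal aPTT is reached (typically 12 u/kg/hr").
- Section 5.2, opening sentence: the infusion escalates "with a minimum target rate of 12 u/kg/hr and until a goal aPTT is achieved".
- Section 5.2, first step: "if a therapeutic level is not achieved the rate will be increased to 10 u/kg/hr 12 hours after study drug initiation".
- Section 5.2, next sentence: a further 2 u/kg/hr step to 12, "until the aPTT goal is reached and then the study drug infusion will be maintained at that level".
- Section 5.2, later text: the protocol allows "adjustments of the rate of infusion up or down from 12 units/kg/hr to achieve a target aPTT".
- Section 6.8, example: at 8 u/kg/hr with an aPTT of 42 seconds, inside the target, "you will always try to get to a minimum of 12 u/kg/hr minimum as long as aPTT is not above the upper goal". The step is marked as needing escalation.

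**The concern.** The example is the only place where the protocol shows sites the titration in units/hr. Its one wrong figure is too high, which is the direction section 5.2 warns against because of bleeding. Bleeding is also the primary safety endpoint.

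The escalation conflict matters more, because it concerns the dosing instruction itself. A patient in range at 8 or 10 u/kg/hr may be held or escalated depending on which text the site follows. Similar patients in the LDIVH arm could then be maintained on different heparin exposure by site. Exposure is the treatment under test, and the day 6 anti-Xa level (below 0.20 versus 0.20 IU/mL or more) defines one of the prespecified LDIVH subgroups in section 1.2.2.

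**Working it through.** **Part (a): the hourly rates.** The inputs are the 80 kg weight and the u/kg/hr steps, all from the 6.8 example. The formula is units/hr = (u/kg/hr) × weight in kg.

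| Step (u/kg/hr) | Printed (units/hr) | Step × 80 | Agrees |
|---|---|---|---|
| 8 | 640 | 640 | yes |
| 10 | 800 | 800 | yes |
| 12 | 960 | 960 | yes |
| 13 (up) | 1040 | 1040 | yes |
| 14 | 1200 | 1120 | no |
| 13 (down) | 1040 | 1040 | yes |

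- Rate implied by the print: 1200 / 80 = 15 u/kg/hr.
- Excess: 1200 − 1120 = 80 units/hr; 80 / 1120 = 7.1%.
- Step up as printed: 1200 − 1040 = 160 units/hr; 160 / 80 = 2 u/kg/hr. The correct step is 1120 − 1040 = 80 units/hr, or 1 u/kg/hr, which is the limit above 12.
- Step down as printed: again 160 units/hr (2 u/kg/hr) instead of 80.

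No other reading gives 1200. It would need a weight of 1200 / 14 = 85.7 kg, while every other line implies exactly 80 kg. The 1800 units/hr cap does not apply either, since at 14 u/kg/hr it binds only from 1800 / 14 = 128.6 kg. The 1200 units/hr in section 6.10.4 belongs to a separate protamine illustration with no weight given.

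**Part (b): the escalation rules applied to the same patient, at 80 kg.**

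| aPTT in range at | Stop at goal aPTT | Section 6.8, if aPTT is never above the upper goal | Ratio |
|---|---|---|---|
| 8 u/kg/hr | 640 units/hr | 960 units/hr | 960 / 640 = 1.50 |
| 10 u/kg/hr | 800 units/hr | 960 units/hr | 960 / 800 = 1.20 |

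For the patient in range at 8, the synopsis and the conditional first step of 5.2 both mean hold, and 6.8 says escalate. For the patient in range at 10, the synopsis says hold. Section 5.2 is less clear there, because its step to 12 carries no condition of its own and only the closing clause suggests stopping early. The opening sentence of 5.2 agrees with 6.8 in both rows, so 5.2 is inconsistent within itself.

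The synopsis also gives the 2 u/kg/hr step without the 1 u/kg/hr limit above 12.

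**The case against.** The case for treating this as editorial is reasonable. The 1200 is a parenthesis in a hypothetical case, and the correct 14 u/kg/hr stands on the same line and is repeated afterwards. All dosing rules are per kg, the figure is below the cap, and an aPTT check follows at 6 hours. Section 6.8 is the operative section, states the 12 u/kg/hr minimum more than once and works through the disputed case. The opening of 5.2 agrees with it, and later text in 5.2 takes 12 as the reference rate and prefers the upper end of the target range. The synopsis is a summary and calls 12 u/kg/hr typical. Under either rule, a patient above the upper aPTT goal is not escalated.

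Much of this stands, and it limits the weight of the point:

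- The printed step down breaks nothing in 6.8, which allows a reduction of 1 to 2 u/kg/hr. It departs only from the 1 u/kg/hr in 6.10.1, and it lowers the dose.
- The 20% case rests essentially on the synopsis.
- The 20% and 50% are conditional differences in rate, with no frequency and no stated effect on bleeding.

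Two things are not answered. The printed rate is wrong and, if used, exceeds a step limit set to avoid bleeding. And 5.2 is a full dosing section, so its conditional first step cannot be set aside as summary wording. For an in-range patient at 8 u/kg/hr, the situation the example itself starts from, it gives the opposite instruction to 6.8.

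**Conclusion.** Both parts hold. The example overstates the rate at 14 u/kg/hr by 80 units/hr (7.1%) and shows a 2 u/kg/hr increase where 1 is the limit. The synopsis and the stepwise sentences of 5.2 conflict with 6.8 for a patient in range below 12 u/kg/hr. At 80 kg the maintained rate differs by up to 50% for a patient in range at 8, provided aPTT does not exceed the upper goal through 12. It differs by 20% for a patient in range at 10, on the synopsis wording.

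This should be fixed but is not critical: the per-kg rate is printed correctly, and aPTT monitoring and the cap contain the risk. The arithmetic rests only on the stated 80 kg. How often the conflict would arise cannot be judged from the protocol.

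**What to change.** 1. In the 6.8 example, change 1200 to 1120 units/hr.
2. Reword the synopsis and the two stepwise sentences of 5.2 to match 6.8: raise by 2 u/kg/hr to 12 u/kg/hr unless aPTT is above the upper goal, then by 1 u/kg/hr only if aPTT is below range. The opening sentence of 5.2 and its preference for the upper end of the range suggest that this is the intended rule, but the clinical leads should confirm it.
3. As minor wording in the same change, use one reduction step in 6.8 and 6.10.1: either 1 u/kg/hr with a 6-hour recheck, or a stated aPTT cut-off for 2. In 6.10.3, replace the moderate label, which 8.5 does not define, with clinically relevant non-major bleeding.

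The cost is a protocol clarification and a notice to sites, with no change to design, sample size or analysis.

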6.9 Study Drug Infusion Safety Monitoring By Investigators

To reduce the risk of bleeding complications in the LDIVH arm of the study, close monitoring of aPTT laboratory values for the LDIVH arm will be done. The aPTT laboratory values for subjects in the LDIVH arm will be collected at regular intervals to monitor anticoagulation effects and adjust the infusion as necessary. aPTT testing will be performed prior to enrollment on all study subjects. aPTT testing will also be done 6 hours after each upwards dose adjustment and at least once daily for the duration of the study drug infusion for patients allocated to the LDIVH treatment group. aPTT testing will occur on control subjects on Infusion day #6 drawn at the same time as the Anti-Xa test listed below.

Anti-Xa testing will occur on patients allocated to both the LDIVH group and the control group at enrollment prior to initiation of the study drug and again on infusion day #6 to help correlate aPTT data between sites. An aPTT value correlating with an anti-Xa value of 0.1 – 0.3 IU/mL is considered within the appropriate target range.

For most hospitals, a CBC (complete blood count) is performed daily for aSAH during admission and the platelet count is inclusive of this test. At a minimum, platelet count will be monitored at least daily for all patients enrolled in the study. We do expect a few cases of type II heparin induced thrombocytopenia within the LDIVH group and/or control group based on the reported incidence of HIT being approximately 0.3-5%. Both the LDIVH group and the control group are at risk for this complication, though we expect the risk to be slightly higher in the LDIVH group. ***We recommend providing a diligent surveillance for this potentially dangerous complication known to be associated with heparin, heparinoid infusions and heparinoid chemical DVT prophylaxis.***

6.10 Study Drug Infusion Rate Adjustments And Emergent Stopping Of Study Drug Infusion

6.10.1 aPTT too high

If the aPTT is found to be higher than the goal target range for patients in the LDIVH study arm and there are no immediate safety concerns related to bleeding or the patient's hemodynamics, then the aPTT value should be redrawn and double-checked. It will be important to have the staff obtaining the blood waste 10 cc prior to collection if obtaining blood from the same IV line as the LDIVH study drug or from a direct puncture of a vein proximal to the IV site for the LDIVH infusion. If the aPTT value is still found to be elevated and out of the acceptable range for patients in the LDIVH arm, the UFH infusion should be decreased by 1 unit/kg/hr lower than the previous dose rate and a follow-up aPTT level should be checked 6 hours later. If this level is again proven elevated above the acceptable amount the UFH infusion should be again decreased by 1 u/kg/hr less than the previous dose and another follow-up aPTT level should be again checked 6 hours later. This process should be repeated until the follow-up aPTT level is within the acceptable range possibly requiring additional LDIVH dose rate adjustments. If the aPTT is at an extremely high, dangerous level (with or without confirmation) then the LDIVH infusion should be stopped immediately (though temporarily) until the aPTT is no longer at an extremely high, dangerous level. We will allow each site investigator to determine what is considered an extremely high, dangerous level for aPTT at their site.

6.10.2 Allergic Reaction

A documented hypersensitivity reaction or high suspicion for hypersensitivity reaction to the LDIVH infusion would necessitate ceasing the study drug infusion temporarily. If the symptoms resolve and high suspicion remains for a serious allergic reaction to the UFH, then the infusion should NOT resume. However, if the symptoms resolve and are discovered to be from an alternate cause and not related to the UFH, then the UFH infusion can be resumed, cautiously, with emergent treatments for a severe allergic response available should they be needed.

6.10.3 Bleeding Complications

Bleeding in all patients should be taken seriously and for those patients in the LDIVH treatment arm we recommend following the 2011 Clinical Practice Guide on Anticoagulant Dosing and Management of Anticoagulant-Associated Bleeding Complications in Adults; Presented by the American Society of Hematology, adapted in part from the: American College of Chest Physicians Evidence-Based Clinical Practice Guideline on Antithrombotic and Thrombolytic Therapy (8th Edition).

<https://www.google.com/url?sa=t&rct=j&q=&esrc=s&source=web&cd=1&ved=0CB8QFjAA&url=http%3A%2F%2Fwww.hematology.org%2FClinicians%2FGuidelines-Quality%2FQuick-Ref%2F525.aspx&ei=yE2PVYj1M8Ks->

[QGYyYHgDw&usg=AFQjCNHVwPINavcTi7zKKG74RuDEnxmHyqQ&bvm=bv.96783405,d.cWw](https://www.ncbi.nlm.nih.gov/pmc/articles/PMC6111111/)

The HASHTI principles of management of anticoagulant-associated bleeding are ideal and should be followed as the clinical scenario necessitates. Details on the HASHTI principles are included in the reference above.

HASHTI

1. **H**old further doses of anticoagulant
2. Consider **A**ntidote
3. **S**upportive treatment: volume resuscitation, inotropes as needed
4. Local or Surgical **H**emostatic measures: topical agents (aminocaproic acid, tranexamic acid)
5. **T**ransfusion (red cells, platelets, FFP as indicated)
6. **I**nvestigate for bleeding source

Patients who have Major Bleeding or Clinically Relevant Non-Major Bleeding and who are allocated to the LDIVH treatment arm should have the study drug infusion stopped immediately, an aPTT level checked, and consideration of administration of protamine sulfate if there is a life-threatening bleeding event. The UFH infusion can resume after the bleeding has been controlled and any aberrant coagulation parameters have been corrected based on the judgment of the local investigator (attending physician). The continuation of the LDIVH infusion should be delayed at least 12 hours after a major bleeding event and at least 6 hours after a moderate event. These are minimum restart times and the actual duration of time to wait after any bleeding event is at the discretion of the treating physician.

